9.2 RECORDING AND REPORTING SAFETY PARAMETERS

9.2.1 Adverse Events

Adverse events (AEs) are defined as any undesirable experience occurring to a patient during the study, whether or not considered related to the IMP. All AEs occurring during the study, i.e., from the date of ICF signature up to and including the end-of-study visit must be recorded on the AE page of the electronic CRF (eCRF). Once emapalumab serum levels are no longer detectable, only serious AEs (SAEs) will be recorded on the AE page of the eCRF.

Medical conditions present at Screening or diagnosed at the Screening visit will be recorded in the medical history section of the eCRF.

An AE which occurs between the Screening visit and the start of first IMP administration will be considered as a pre-treatment AE.

Any AE that occurs after the start of first IMP administration will be considered as a Treatment Emergent Adverse Event (TEAE), including the specific situations described below. AEs are collected after signing of ICF up to Study Completion or until serum levels of emapalumab are no longer detectable (whichever occurs first). After elimination of emapalumab only SAEs will be reported.

Should a pre-existing medical condition worsen (clinically significant change in intensity or frequency), it must be recorded as an AE in the eCRF and, depending on the time of its occurrence, will be considered as a pre-treatment AE or a TEAE. Should a medical condition recorded as a pre-treatment AE worsen after start of IMP administration, it will be recorded in the eCRF as a separate TEAE, specifying `Worsening of xxx`.

For all AEs, the following will be assessed and recorded: onset and end dates (and -when relevant- time), intensity, seriousness, relationship to IMP, action taken regarding IMP, any treatment received, and outcome.

Intensity of AEs will be graded on a three-points scale (mild, moderate, severe) using the modified World Health Organization (WHO) toxicity scale (Grade 3 and 4 are considered to be the severe grade). If AE severity is not mentioned in the scale, assessment will be made using the following definitions:

- Mild: Discomfort noticed but no disruption of normal activity
- Moderate: Discomfort sufficient to reduce or affect normal daily activity
- Severe: Inability to work or perform normal daily activity

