9.2.4 Managing Abnormal Laboratory Test Values

All laboratory tests (hematology, coagulation, blood chemistry) will be captured in the database from the local laboratory.

Laboratory test abnormalities must be considered as AEs and recorded on specific AE pages of the CRF only if they:

- require specific intervention for correction, or
- lead to a change in study medication (e.g., dose modification, interruption or permanent discontinuation), or
- qualify as grade 4 severity as per modified WHO toxicity scale

If a laboratory test abnormality leads to a new clinical diagnosis, the new clinical diagnosis should be reported as an AE rather than the laboratory abnormality.

Laboratory test abnormality that qualifies as an AE as per the definition above, will follow the AE/SAE reporting process described in this section.

Laboratory abnormalities which are considered to be part of HLH signs and symptoms (see Section 9.2.1) will not be reported as AEs. If laboratory abnormalities are indicative of an HLH reactivation or worsening, the reactivation or worsening of HLH will be reported as the AE, and not the laboratory abnormalities themselves.

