If a character parameter needed for the response assessment (i.e. Spleen Assessment, CNS) is missing, last observation carried forward method will be used to estimate the missing value - i.e., the last observed value within a maximum of 7 consecutive days before the missing period will be used.

In case that, after imputation, data is still missing in any of the criteria considered for the definition of response, a Complete Response cannot be adjudicated.

[figure not shown]
- If the maintenance of response (of at least 4 days) cannot be confirmed due to missing data, the response will be assumed to be lost. In case of calculation of duration of response (i.e. durability of first response) the next response period will be considered. If none of the subject's responses could have been confirmed to last for at least 4 days or only one response was documented which could not have been confirmed to last for at least 4 days, the duration of response will be set to 1 day applying a conservative imputation strategy.
- Since data relevant to CNS assessment has been collected at irregular time-points (based on individual patient conditions), the investigators assessment of CNS status will be carried-forward until the time-points of relevance for response analysis

For descriptive statistics on the evolution over time of clinical signs characterizing HLH disease, the time windows listed in Table 1 and Table 2 will be applied in the case that a parameter is not available on the specified study day.

For any assessment, if there is more than one observation during the visit window, the closest value (within the visit window) to the target day will be chosen first. In the case that there are 2 equidistant values to the study day of interest, the observation that is after the study day in question will be selected.

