6.1.9.4. Efficacy Parameters

- Overall Response at EOT or Week 8 = achievement (yes/no) of either Complete or Partial Response or HLH improvement at EOT or the Week 8 assessment, whichever occurs earlier.
- Overall Response at start of conditioning for HSCT = achievement (yes/no) of either Complete or Partial Response or HLH improvement at start of conditioning of HSCT (date of start of conditioning) or last emapalumab if HSCT is not performed.

The definition of the Overall Response for the primary endpoint is detailed in Table 6 along with additional clarifications.

The definition of the Overall Response used in the supplementary analysis is detailed in Table 7.

Response for Primary Endpoint	Definition	Additional Clarifications
Complete Response	Complete Response is adjudicated if: - No fever = body temperature < 37.5 °C - Normal spleen size - No cytopenia = Absolute Neutrophil Counts $\geq 1.0 \times 10^{9}$ /L and platelet count $\geq 100 \times 10^{9}$ /L [absence of G-CSF and transfusion support must be documented for at least 4 days to report no cytopenia] - No hyperferritinemia = serum ferritin level is < 2000 µg/L - No evidence of coagulopathy, i.e., normal D-Dimer and/or normal (> 150 mg/dL) fibrinogen levels - No neurological and CSF abnormalities attributed to HLH - No sustained worsening of sCD25 (as indicated by at least two consecutive measurements that are > 2-fold higher than baseline)	 All HLH parameters that were abnormal at baseline must be normalized No AEs relating to organ failure All other parameters that were normal at baseline must still meet the definition of normalized Normal spleen size confirmed by abdominal ultrasound (US) whenever possible based on the splenomegaly not present; if US not performed physical examination will be used Normal D-Dimer levels are <= 500 ug/L No neurological abnormalities attributed to HLH = "normal" neurological assessment by investigator in the neurological examination page (without findings in brain imaging (Brain MRI/Brain CT/cranial ultrasound) or AEs indicative of "CNS involvement" (Appendix 15.3) No CSF abnormalities = no AE indicative of "CSF abnormalities" (Appendix 15.3)

[figure not shown]
Response for Primary Endpoint	Definition	Additional Clarifications

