Partial Response	 Partial Response is adjudicated if: At least 3 of the HLH clinical and laboratory abnormalities (including CNS abnormalities) meet the above mentioned criteria for "Complete Response" In the case of "reactivated patients" who enter the study with 3 abnormal HLH features, Partial Response is adjudicated if at least 2 parameters normalize 	If a patient is not considered as "reactivated" or a patient is considered "reactivated" with 4 or more abnormal HLH features upon entry to the study and at least 3 of the HLH clinical and laboratory abnormalities (including CNS abnormalities) meet the above-mentioned criteria for "Complete Response" Partial Response is adjudicated.
	 In case of reactivated patients who enter the study with 2 abnormal HLH clinical and laboratory parameters only, Partial Response is adjudicated if one of the 2 parameters normalizes There is no progression of other aspects of HLH disease pathology 	For all patients: no progression of other aspects of HLH disease pathology is assessed by absence of AEs indicating organ failure including no worsening of sCD25 levels.

Response for Primary Endpoint	Definition	Additional Clarifications
HLH Improvement	 HLH Improvement is adjudicated if: Improvement (>50% change from baseline or normalization) of at least 3 HLH clinical and laboratory abnormalities (including CNS abnormalities). In the case of "reactivated patients" who enter the study with only 2 abnormal HLH features, a change from baseline greater than 50% for both will define HLH as improved. 	 Definition of 50% improvement from baseline: Spleen size decreased by 50%, as recorded in cm from costal margin at physical examination. Absolute Neutrophil Count increased by 50%, if G-CSF has not been administered in the previous 4 days and Platelet count increased by 50%, if no platelet transfusion has been administered in the previous 4 days Ferritin decreased by 50% Fibrinogen increased by 50% or D-Dimer decreased by 50% Normalization of CNS abnormalities = normal neurological assessment by investigator without findings in brain imaging (Brain MRI/Brain CT/cranial ultrasound), CSF analysis or AEs indicative of "CNS involvement" or "CSF abnormalities"
No Response	If a subject does not meet the criteria for at least HLH improvement, response is categorized as "No Response"	
Abbreviations: CNS, c lymphohistiocytosis	entral nervous system; CSF, cerebrospinal fluid; G-CSF, gr	anulocyte-colony-stimulating factor; HLH, hemophagocytic

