16.2. Concomitant Medications for HSCT Conditioning

Table 19: Concomitant HSCT Conditioning Medication Preferred Terms

ATC Level 4	Preferred Code	Preferred Text
L01AA	00021101001	CYCLOPHOSPHAMIDE
201121	00006401001	MELPHALAN
L01AB	00036801001	BUSULFAN
	00418901001	TREOSULFAN
L01AC	00053501001	ТНІОТЕРА
L01BB	02122001001	CLOFARABINE
LUIDD	01004601001	FLUDARABINE
	01004602001	FLUDARABINE PHOSPHATE
L01BC	00146201001	CYTARABINE
L01BC	00511901001	ETOPOSIDE
20120	00511902001	ETOPOSIDE PHOSPHATE
L01XC	01402501001	RITUXIMAB
L04AA	01268601001	ALEMTUZUMAB
Lonni	00575401001	ANTITHYMOCYTE IMMUNOGLOBULIN
	00575402001	ANTITHYMOCYTE IMMUNOGLOBULIN (RABBIT)
	02082701001	ANTILYMPHOCYTE IMMUNOGLOBULIN

16.3. Disease Indicating Central Nervous System (CNS) Involvement / CSF abnormalities by Medical History/AE Preferred Term and Code

[figure not shown]
Preferred Term Code	Preferred Term
10029818	Nuclear magnetic resonance imaging brain abnormal
10059703	CSF test abnormal
10053805	CSF white blood cell count increased
10011522	CSF cell count increased
10035551	Pleocytosis
10012559	Developmental delay
10056832	Neurological examination abnormal
10047641	VIth nerve paralysis
10020745	Hyperreflexia
10041962	Status epilepticus
10039906	Seizure
10021118	Hypotonia
10002948	Aphasia
10029202	Nervous system disorder
10017577	Gait disturbance
10048334	Mobility decreased
10008096	Cerebral atrophy
10015037	Epilepsy
10071066	Posterior reversible encephalopathy syndrome
10022840	Intraventricular haemorrhage

The overall response criterion 'No neurological and CSF abnormalities attributed to HLH' is not fulfilled during the time period in which any of the above listed AEs is present or the assessment on neurological examination CRF is 'abnormal' with comment 'CNS involvement'.

AD-ST-33.06 Effective date: 12-Nov-2020

Statistical Analysis Plan, Sponsor Sobi AG

Protocol Number NI-0501-09 PCN Number 176784

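### Complete Response judges CSF disease only by the absence of a listed adverse event, so CSF-only disease found at Screening that persists unchanged meets the criterion

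*SAP*

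**What the plan says.** Protocol Table 4 makes the absence of neurological and CSF abnormalities attributed to HLH a condition of CR. The SAP puts this into operation in several places.

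- **SAP 6.1.9.4, Tables 6 and 7, CR row.** The neurological half needs a normal investigator assessment, no brain imaging finding and no AE indicating CNS involvement. The CSF half is "No CSF abnormalities = no AE indicative of" CSF abnormalities.
- **Same tables, PR row.** CNS is one of the features that may count as normalised, judged by the CR criteria.
- **Same tables, HLH Improvement row.** CNS is normalised when the neurological assessment is normal, without "findings in brain imaging (Brain MRI/Brain CT/cranial ultrasound), CSF analysis or AEs indicative of" CNS involvement or CSF abnormalities.
- **SAP Appendix 16.3.** The combined criterion "is not fulfilled during the time period in which any of the above listed AEs is present or the assessment on neurological examination CRF" shows an abnormal result, with CNS involvement given as the comment.
- **SAP 10.2.3.** CSF protein, red cells, white cells and neopterin are collected but only listed.
- **Protocol 9.2.1.** "Medical conditions present at Screening or diagnosed at the Screening visit will be recorded in the medical history section of the eCRF".
- **SAP 6.1.4, response throughout the study.** One bullet limits carry-forward of spleen and CNS values to 7 days. Another says "the investigators assessment of CNS status will be carried-forward until the time-points of relevance for response analysis", with no limit. The EOT/Week 8 assessment has a separate rule: the closest value up to 8 days from the target day.

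**The concern.** The protocol's criterion is about the state of the CSF. The SAP's CR rule is about whether a site filed an adverse event. The two differ for disease that was present before treatment and has not changed: it belongs in medical history and gives no reason to open an AE. The lowest response category then applies a stricter CSF test than the highest, and the SAP gives no reason for this.

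At stake is mainly the correctness of the CR count, which is reported as a component of the primary endpoint. In a narrower set of patients the primary yes/no classification itself could change. Table 7 repeats the AE-only line, so the supplementary analysis cannot reveal the problem.

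**Working it through.** The plan states no figure on this point, so the check is a trace of the text followed by a scale calculation.

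**1. One patient through the rules.** Take a child with abnormal CSF at Screening, a normal neurological examination, no brain imaging finding, and the same CSF abnormality on repeat.

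| Source | What happens |
|---|---|
| Protocol 8 and 8.1 | CSF is analysed at Screening if coagulation allows; a repeat is foreseen to follow an abnormal result |
| Protocol 9.2.1 | The Screening finding is recorded as medical history; without worsening, no AE arises |
| SAP Table 6, CR, CSF line | No listed AE, so the criterion is met |
| SAP Table 6, CR, neurological line | Normal examination, no imaging finding, no AE, so the criterion is met |
| SAP Appendix 16.3 | No listed AE and no abnormal examination, so the criterion is not failed |
| SAP Table 6, HLH Improvement | A CSF analysis with findings, so CNS is not normalised |
| Protocol Table 4, CR | A CSF abnormality attributed to HLH persists, so the criterion is not met |

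The same patient passes on the CNS feature for CR and fails on it for HLH Improvement. The result that shows persistence is in the database.

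**2. Does the Appendix 16.3 heading close the gap?** It reads "CSF abnormalities by Medical History/AE Preferred Term and Code", so history terms were in view. The operative sentence under the list names AEs and the examination only. If history terms mark CNS as abnormal at baseline, the feature would later count as normalised simply because no AE exists.

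**3. When does the primary endpoint change?** CR, PR and HLH Improvement all count as response. A patient who loses CR but has three other normalised features, or enough improved ones, is still a responder. A responder is created only if (a) CSF disease counts as a baseline abnormality and (b) CNS is the deciding feature under PR: the third of three, the second of two needed in a reactivated patient with three abnormal features, or the one needed in a reactivated patient with two. PR must also not be blocked by a listed organ-failure AE or sCD25 worsening. The SAP does not say how condition (a) is decided. Section 7.3 cites Appendix 15.4 for baseline CNS involvement, and no such appendix exists.

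**4. Scale, for assumed counts.** Inputs from SAP 3.2 and 8.1: n = 34, null rate 0.40, one-sided 0.025, exact binomial.

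- P(X ≥ 20) = 0.0205 and P(X ≥ 19) = 0.0444, so success needs 20 responders.
- One patient is 1/34 = 2.9 percentage points.
- If k patients are always scored as responders, type I error is P(X ≥ 20 − k) with n = 34 − k: 0.031, 0.046 and 0.068 for k = 1, 2, 3.
- At n = 41 success needs 24 (0.0126), and the same k give 0.019, 0.028 and 0.041.

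These figures hold for any misclassified patient. The value of k is an assumption; the documents give none, and it may be zero.

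**The case against.** The strongest defence is that the gap is narrow and other safeguards exist. Much of this stands.

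- **AE reporting is not closed to CSF findings.** A reader might infer from Protocol 9.2.4 ("Laboratory abnormalities which are considered to be part of HLH signs and symptoms (see Section 9.2.1) will not be reported as AEs") that HLH-related CSF abnormalities are barred from AE data. The documents do not support that. The section opens by limiting itself to hematology, coagulation and blood chemistry, and the HLH signs listed as examples in 9.2.1 do not name CSF. Appendix 16.3 lists CSF terms, so a site may record one. Worsening of a pre-existing condition must be recorded, and HLH worsening or reactivation is an AE. What remains is pre-existing, unchanged disease.
- **CR is not looser on imaging.** The CR row also requires no brain imaging finding. Within the tables, the difference is CSF analysis alone.
- **No automatic gain under PR.** A reader might infer that every patient with CSF-only disease gets a free normalised feature. That needs CSF disease to be abnormal at baseline by one source and normal later by another. If the AE rule also governs baseline, the feature never enters the count.
- **The CR row requires every parameter abnormal at baseline to normalise.** This does not help, because CSF normality is itself defined as no AE.
- **The investigator could mark the examination as abnormal with CNS involvement.** This is possible, but it relies on an examination form to carry a laboratory result already collected elsewhere.

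A repeat puncture after Screening is done only if clinically indicated. Holding CSF abnormal indefinitely until a normal repeat would therefore let the absence of a test decide response. That objection limits the remedy.

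**Conclusion.** The concern holds in a limited form. As written, Tables 6 and 7 let CSF-only disease that was present at Screening and persists unchanged meet the CR criterion, contrary to Protocol Table 4 and to the HLH Improvement row of the same tables. This rests on CSF findings at Screening being filed as medical history, as Protocol 9.2.1 directs, and on a normal examination and no imaging finding.

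The expected effect is CR in place of a lower category. An effect on the primary endpoint is possible but conditional on an undefined baseline rule and on CNS being the deciding feature under PR. The documents give no count of such patients, so the p-values above show only what one wrong classification could do near the success boundary. They do not estimate bias in this trial. The correction is worth making before database lock.

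**What to change.** - **One definition.** In Tables 6 and 7, use a single CNS/CSF rule for CR, PR and HLH Improvement, taking the sources in the HLH Improvement row: normal neurological examination, no finding attributed to HLH in brain imaging or CSF analysis, and no listed AE. Say who or what decides that a CSF result is a finding, since 10.2.3 gives no limits.
- **Baseline.** Use the same sources to decide whether CNS is abnormal at baseline.
- **Timing.** Where CSF was abnormal at baseline, use the most recent CSF result available before the assessment. Reconcile this with the 8-day EOT/Week 8 rule and with the two carry-forward bullets in 6.1.4.
- **Appendix.** Make Appendix 16.3 match, including imaging and the handling of an abnormal examination, and correct the references to 15.3 in Tables 6 and 7.
- **Sensitivity analysis.** Count patients with abnormal baseline CSF and no repeat as not normalised on that feature.

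The cost is SAP wording and programming on data already collected. Some patients may move from CR to a lower category; the documents do not allow that number to be estimated.

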6.3.3 Other Concomitant Therapies

Intravenous immunoglobulin (IVIG) are only allowed as replacement treatment (i.e., not at doses expected to produce an immunomodulatory effect) according to the clinical judgement of the Investigator. Any IVIG infusion within the previous 4 weeks prior to Screening, as well as any infusion during emapalumab treatment, should be documented in the Case Report Form (CRF; dose, date of administration).

Analgesic treatment, transfusion of blood products, electrolyte and glucose infusions, IV parenteral nutrition, inotropic support, antibiotics, anti-fungal and anti-viral treatment, hemofiltration or hemodialysis, as well as general supportive care (e.g., gastro-protective agents, anti-hypertensive etc.) are permitted within the study.

The use of any prescription or over-the-counter medication, including herbal and homeopathic preparations with the exception of multi-vitamins, needs to be notified to the Investigator.

Contraception guidance: see Section 6.4.

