3.2. Sample Size and Power

The sample size calculation is based on the primary efficacy endpoint of Overall Response. Assuming an Overall Response Rate of 65%, a minimum of 34 treated patients is required to show a significant improvement above 40% with 85% power using an exact binomial test at a one-sided significance level of 2.5%. A drop-out rate of 20% may be expected, hence a total maximum of 41 patients may be enrolled. Due to the rarity of pHLH, recruitment is competitive across all European and North American sites in order to gather data in a reasonable timeframe.

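### The 4-day support-free condition covers neutrophils and platelets but not fibrinogen, so product-raised fibrinogen can count towards Partial Response or HLH Improvement

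*SAP*

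**What the plan says.** The primary endpoint counts Complete Response, Partial Response and HLH Improvement alike (SAP 2.2.1.1). SAP 6.1.9.4, Table 6 defines the items.

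- Counts, normalisation: "absence of G-CSF and transfusion support must be documented for at least 4 days to report no cytopenia".
- Counts, 50% rule for HLH Improvement: "Absolute Neutrophil Count increased by 50%, if G-CSF has not been administered in the previous 4 days", with a parallel condition on platelets that refers to platelet transfusion.
- Coagulopathy, normalisation: "No evidence of coagulopathy, i.e., normal D-Dimer and/or normal (> 150 mg/dL) fibrinogen levels".
- Coagulopathy, 50% rule: "Fibrinogen increased by 50% or D-Dimer decreased by 50" per cent.

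Neither coagulopathy line carries a condition about recent blood products. Protocol Table 4 has the same coagulopathy definition, and SAP Table 7 (supplementary analysis) repeats both lines. Protocol 6.3.3 lists among the permitted treatments "Analgesic treatment, transfusion of blood products, electrolyte and glucose infusions", with no timing limit around response assessments.

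**The concern.** Table 6 already accepts that supportive products can imitate a response, which is why it guards neutrophils and platelets. Fibrinogen is open to the same problem, because plasma or another fibrinogen-containing product raises the measured value without any change in the disease. (That is general knowledge; the documents do not discuss it.) Because the two markers are joined by and/or in one line and by or in the other, a D-dimer that is still abnormal does not stop the item being met.

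At stake is whether some patients enter the numerator of the primary endpoint because of a transfusion. The trial has one arm and a fixed 40% reference, so no control group would carry the same misclassification and offset it.

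**Working it through.** **1. The plan's own figure.** SAP 3.2 states: "Assuming an Overall Response Rate of 65%, a minimum of 34 treated patients is required to show a significant improvement above 40% with 85% power". The test named there is the exact binomial, one-sided at 0.025. With X ~ Binomial(34, 0.40), P(X ≥ k) = Σ C(34, x) 0.4^x 0.6^(34−x), summed over x from k to 34.

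- P(X ≥ 19) = 0.0444 and P(X ≥ 20) = 0.0205, so the test succeeds at 20 or more responders (58.8%).
- Exact power at 65% is P(X ≥ 20 | 0.65) = 0.826, not 0.85. The figure of 34 does follow from the normal approximation: [(1.960√0.24 + 1.036√0.2275)/0.25]² = 33.85, rounded up. This shortfall is a separate matter and does not bear on the present point.

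**2. Where the 4-day condition applies in Table 6.**

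| Item | Normalisation | 50% rule |
|---|---|---|
| Neutrophils | no G-CSF or transfusion, 4 days | no G-CSF, 4 days |
| Platelets | no G-CSF or transfusion, 4 days | no platelet transfusion, 4 days |
| Fibrinogen | none | none |

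**3. What the coagulopathy item can contribute.**

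- Partial Response: one of 3 normalised items. For reactivated patients entering with 3 abnormal features it is one of the 2 needed; for those entering with 2 it can be the only one needed.
- HLH Improvement: one of 3 improved items. Reactivated patients entering with 2 features need both to improve, so fibrinogen alone cannot decide it.
- Table 7 extends the reduced Partial Response counts (2 of 3, 1 of 2) to patients who are not reactivated, so in the supplementary analysis the item can be decisive in more patients.

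**4. Whether another rule catches it.** Sensitivity analyses 1 to 5 (SAP 8.1) deal with deaths, early withdrawals, other HLH treatments and major protocol deviations, not blood products. The rule for missing EOT/Week 8 values (SAP 6.1.4) takes the closest value within 8 days, unscheduled visits included, and does not ask about products. Transfusions are only listed (Listing 16.2.9.9).

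**5. Size at the boundary.** At n = 34, 20 responders give p = 0.0205 and 19 give p = 0.0444, so one reclassified patient changes the result there. Away from it one patient does not: 22 responders (64.7%, close to the planned rate) give p = 0.0031, and 22 − 19 = 3 would have to be reclassified.

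**6. Illustration, resting on an assumption.** Suppose the true rate is 40%, a share m of true non-responders is scored as response through product-raised fibrinogen, and nothing acts in the other direction. The apparent rate is 0.40 + 0.60m, and the expected number misscored at n = 34 is 20.4m.

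| m | Apparent rate | Misscored, n = 34 | P(success), n = 34 (≥ 20) | P(success), n = 41 (≥ 24) |
|---|---|---|---|---|
| 0 | 0.400 | 0 | 0.0205 | 0.0126 |
| 2% | 0.412 | 0.4 | 0.0288 | 0.0188 |
| 5% | 0.430 | 1.0 | 0.0462 | 0.0327 |
| 10% | 0.460 | 2.0 | 0.0922 | 0.0732 |

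Nothing in the documents indicates which row is realistic.

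**The case against.** The case for leaving the plan alone has several parts.

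- **Complete Response.** A reader might infer that all three response levels are exposed. They are not equally so. Complete Response also requires the cytopenia item, whose transfusion wording is not limited to any product; read plainly, plasma within 4 days blocks it. This stands. Partial Response and HLH Improvement do not require that item.
- **Direction.** A reader might infer that the bias can only favour response. SAP 6.1.1 takes the last value before first dose as baseline. A product given just before then can hide a low fibrinogen or make a 50% rise harder to reach, and both work against response. This stands, so the net direction is not known.
- **Existing bars on Partial Response.** An organ-failure AE or worsening sCD25 rules it out, and SAP 16.4 includes Condition aggravated, the term SAP 6.1.9.4 uses for HLH reactivation. Some worsening patients are therefore already excluded. This narrows the route, but Table 6 puts no such bar on HLH Improvement.
- **Unknown frequency.** The documents name neither plasma nor fibrinogen concentrate and give no rate of use. Plasma falls under blood products; placing a concentrate there is an inference. The comparison of 20 with 19 responders would serve any criticism of the endpoint equally well. This limits the claim about size, not the claim about the rule.
- **Fidelity to the protocol.** Table 6 follows Protocol Table 4, so rewriting it would change the protocol-defined endpoint. This stands and shapes the fix.

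**Conclusion.** The gap is real but narrower than it first looks. Under the plan as written, a fibrinogen value raised by a recent product can count as a normalised abnormality for Partial Response, or as a normalised or improved one for HLH Improvement, and no planned analysis shows how often that decides the result. It changes the response only when coagulopathy is the last item needed, and it changes the primary test only if the count lies close to 20 of 34.

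A reader might go further and infer from the illustration that the type I error of the primary test is inflated to some particular level. The documents do not support that: the share misscored is assumed, and the opposing baseline effect is left out. The conclusion rests on two premises, that such products raise measured fibrinogen and that some patients receive them near the EOT/Week 8 assessment. The first is general knowledge; the second is permitted by the protocol but not quantified.

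**What to change.** Keep the primary endpoint as the protocol defines it. Add to SAP 8.1, with matching entries in SAP Table 3 and the planned tables, a prespecified sensitivity analysis in the All Treated Analysis Set using the same exact test:

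- Fibrinogen normalisation, or a 50% increase, does not count if plasma or a fibrinogen-containing product was given in the previous 4 days. The window is the one already used for counts; the documents offer none specific to fibrinogen.
- Inside that window, a baseline coagulopathy counts only if D-dimer was itself abnormal at baseline and has normalised or, for HLH Improvement, fallen by 50%. Otherwise the item is scored as not improved. Requiring an abnormal baseline D-dimer avoids crediting a patient whose only abnormality was low fibrinogen.
- Flag patients who received such a product in the 4 days before the baseline fibrinogen value, so that the opposite bias is visible too.

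Derive this from the transfusion and concomitant-medication data. First confirm that product type is recorded, because the listing is titled only Transfusion. The cost is one extra derivation and table, and a response rate that may be slightly lower in that analysis. Treatment, sample size, alpha and the critical value do not change.
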